7.1.3. Clinical Laboratory Tests

All clinical laboratory tests will be graded according to the [Appendix 7](#) from the study protocol. Grade 2 or higher laboratory events will be tabulated by number and percentage of subjects with the event by study phase.

Change from baseline in hematology, fasting chemistry, fasting lipid profile, and coagulation profile will be summarized by visit. For the definition of baseline, refer to Section [10.5.2](#). Urinalysis and urine chemistry results will be summarized by visit as either categorical values or as continuous values, depending on the type of the parameter.

For each lab test, shift from baseline table will be provided based on toxicity grade, both by visit and for the shift to maximum toxicity grade in each study phase. Data collected at unscheduled visits will not be included in the by-visit summary, but will be used in the calculation of maximum grade in each study phase. Subjects having both high and low values will be counted in both High and Low categories for the summary by study phase.

All lab data, as well as lab data for subjects with Grade 2 or higher abnormalities, will be listed. Abnormal data will be listed with an indicator, which is low/high relative to normal range. All laboratory results from local labs, if any, will be listed only

[Table 5](#) provides an overview of the planned lab test analyses, with full details of data displays being presented in [Appendix 14](#): List of Data Displays.

Table 5 Overview of Planned Lab Test Analyses

Display Type	Absolute				Change from Baseline			
	Summary		Individual		Summary		Individual	
	T	F	F	L	T	F	F	L
Laboratory Test Analyses								
Grade 2 or high laboratory events	Y							
Clinical Chemistry				Y	Y			
Hematology				Y	Y			
Fasting Lipid Profile				Y	Y			
Coagulation Profile				Y	Y			
Urinalysis and Urine Chemistry	Y			Y	Y			
Other lab data including local lab				Y				

- T = Table, F = Figure, L = Listing, Y = Yes display generated.
- Stats Analysis = Represents TFL related to any formal statistical analyses (i.e. modelling) conducted.
- Summary = Represents TFL related to any summaries (i.e. descriptive statistics) of the observed raw data.
- Individual = Represents FL related to any displays of individual subject observed raw data.

7.1.4. Vital Sign Assessments

Change from baseline in vital signs, including temperature, systolic and diastolic blood pressure, and pulse rate and respiratory rate will be summarized by study visit. For the

definition of baseline, refer to Section 10.5.2. Shift from baseline table (with respect to clinical concern range) will also be provided.

All vital signs, as well as vital signs for subjects with abnormalities of potential clinical importance, will be listed with an indicator, which is low/high relative to clinical concern range.

Table 6 provides an overview of the planned vital sign analyses, with full details of data displays being presented in Appendix 14: List of Data Displays.

Table 6 Overview of Planned Vital Sign Analyses

Display Type	Absolute				Change from Baseline			
	Summary		Individual		Summary		Individual	
	T	F	F	L	T	F	F	L
Vital Signs								
Vital signs				Y	Y			

NOTES:

- T = Table, F = Figure, L = Listing, Y = Yes display generated.
- Stats Analysis = Represents TFL related to any formal statistical analyses (i.e. modelling) conducted.
- Summary = Represents TFL related to any summaries (i.e. descriptive statistics) of the observed raw data.
- Individual = Represents FL related to any displays of individual subject observed raw data.

7.1.5. Death

Both primary and secondary causes, if any, will be listed for each deceased participant.

Table 7 provides an overview of the planned death analyses, with full details of data displays being presented in Appendix 14: List of Data Displays.

Table 7 Overview of Planned Death Analyses

Display Type	Data Displays Generated						
	Stats Analysis			Summary		Individual	
	T	F	L	T	F	F	L
Death Analysis							
Death							Y

NOTES:

- T = Table, F = Figure, L = Listing, Y = Yes display generated.
- Stats Analysis = Represents TFL related to any formal statistical analyses (i.e. modelling) conducted.
- Summary = Represents TFL related to any summaries (i.e. descriptive statistics) of the observed raw data.
- Individual = Represents FL related to any displays of individual subject observed raw data.

7.2. Tolerability Analyses of CAB LA

The tolerability analyses will be based on the safety injection population, unless otherwise specified. All summary data and statistics are calculated from available data, unless otherwise specified.

To assess tolerability of CAB LA, the proportion (with 95% confidence interval) of participants who terminate from receiving injections prior to the full course due to AE, intolerability of injection, frequency of injections, or burden of procedures related to injections will be calculated out of those participants that received at least one injection.

A questionnaire will also be used to assess participant tolerability and satisfaction to the treatment. For each question, the responses will be summarized by the proportion of participants reporting the response out of all those that answered the question. An overall treatment satisfaction score will be calculated for each participant.

Total score is defined as the sum of the scores for individual questions. If less than or equal to 50% of the questions for an individual participant are missing, the missing total scores will be estimated using the average of the existing questions multiplied by twelve; if more than 50% of the questions for an individual participant are missing, the total score will not be estimated and will be considered as missing. When calculating total scores, question ^{CCI} [REDACTED]

^{CCI} [REDACTED] will be used and question ^{CCI} [REDACTED]

^{CCI} [REDACTED]

^{CCI} [REDACTED] will be excluded.

Table 8 provides an overview of the planned tolerability analyses, with further details of data displays being presented in Appendix 14: List of Data Displays.

Table 8 Overview of Planned Tolerability Analyses

Display Type	Data Displays Generated						
	Stats Analysis			Summary		Individual	
	T	F	L	T	F	F	L
CAB LA Discontinuation							
Injection Discontinuation Rate				Y			Y
Treatment Satisfaction Questionnaire							
Each question in the questionnaire				Y			Y
Treatment total satisfaction score				Y			Y

NOTES:

- T = Table, F = Figure, L = Listing, Y = Yes display generated.
- Stats Analysis = Represents TFL related to any formal statistical analyses (i.e. modelling) conducted.
- Summary = Represents TFL related to any summaries (i.e. descriptive statistics) of the observed raw data.
- Individual = Represents FL related to any displays of individual subject observed raw data

7.3. Primary Pharmacokinetic Analyses**7.3.1. Overview of Planned Primary Pharmacokinetic Analyses**

The primary pharmacokinetic (PK) analyses will be based on the Oral PK and Injection (Week 41) PK populations, unless otherwise specified.

[Table 9](#) provides an overview of the planned efficacy analyses, with full details of data displays being presented in [Appendix 14](#): List of Data Displays.

Table 9 Overview of Planned Primary Pharmacokinetic Analyses

Display Type	Untransformed							Log-Transformed						
	Stats Analysis			Summary		Individual		Stats Analysis			Summary		Individual	
	T	F	L	T	F	F	L	T	F	L	T	F	F	L
Oral/Injection														
PK Concentrations				Y	Y ^[1]	Y ^[1]	Y							
Plasma PK Parameters	Y			Y			Y			Y	Y			

NOTES:

- T = Table, F = Figure, L = Listings, Y = Display generated.
- Stats Analysis = Represents TFL related to any formal statistical analyses (i.e. modelling) conducted.
- Summary = Represents TFL related to any summaries (i.e. descriptive statistics) of the observed raw data.
- Individual = Represents FL related to any displays of individual subject observed raw data.

^[1] Linear and Semi-Logarithmic plots will be created on the same display.

7.3.2. Primary Drug Concentration Measures

Refer to [Appendix 5](#): Data Display Standards & Handling Conventions (Section [10.5.3](#) Reporting Process & Standards).

7.3.3. Primary Pharmacokinetic Parameters

7.3.3.1. Deriving Primary Pharmacokinetic Parameters

- Refer to [Appendix 5: Data Display Standards & Handling Conventions](#) (Section [10.5.3 Reporting Process & Standards](#)).
- The pharmacokinetic parameters will be calculated by standard non-compartmental analysis according to current working practices and using Phoenix WinNonlin Version 6.4 or higher.
- All calculations of non-compartmental parameters will be based on actual sampling times, and all concentrations will be included in the estimation of PK parameters regardless of whether samples are collected within the specified time window or not.
- Pharmacokinetic parameters described in [Table 10](#) will be determined from the plasma concentration-time data, as data permits.

Table 10 Derived Primary Pharmacokinetic Parameters

Parameter	Parameter Description
AUC(0- τ)	Area under the concentration-time curve over the dosing interval will be calculated using the linear trapezoidal rule for each incremental trapezoid and the log trapezoidal rule for each decremental trapezoid.
C _{max}	Maximum observed concentration, determined directly from the concentration-time data.
t _{max}	Time to reach C _{max} , determined directly from the concentration-time data.
C _{τ}	Observed concentration at the end of the dosing interval, determined directly from the concentration-time data.
t _{1/2}	Terminal absorption elimination half-life will be calculated as: $t_{1/2} = \ln 2 / \lambda_z$
λ_z	Terminal absorption elimination rate constant
CL/F	Clearance (adjusted for bioavailability, F) will be calculated as: $CL/F = \text{Dose} / AUC(0-\tau)$
V _z /F	Volume of distribution (adjusted for bioavailability, F) will be calculated as: $V_z/F = CL / \lambda_z$

NOTES:

- Additional parameters may be included as required.
- λ_z , CL/F, V_{ss} and t_{1/2} will be determined for the Oral PK population only in the primary analysis; these parameters will be further explored for the Injection (Week 89) PK population (Section [8.1.3.1](#)).

7.3.3.2. Statistical Analysis of Primary Pharmacokinetic Parameters

The following pharmacokinetic statistical analyses will only be performed, if sufficient data is available (i.e. if subjects have well defined plasma profiles).

Pharmacokinetic Statistical Analyses
Endpoint(s)

 Plasma primary PK endpoints include C_{τ}, as data permit
Model Specification

Assessment of Accumulation (Injection Phase only):
 
 To determine accumulation of plasma CAB following treatment with CAB LA, the log-transformed C_{τ} values for CAB will be analyzed using a mixed effects model (ANOVA) as appropriate to the study design, fitting fixed effect terms for visit and treating subject as a random effect. Point estimates and 90% confidence intervals (CIs) for the differences of interest (i.e. accumulation of CAB based on $AUC(0-\tau)$: Week 34 / Week 6) will be constructed using the residual variance. 
Attainment of Steady state (Injection Phase only):
 
 If data permit, a statistical analysis of steady-state trough concentrations (C_{τ}) will be performed after log-transformation of C_{τ} on Weeks 17, 25, 33, and 41 to evaluate whether steady state was achieved using the Helmert transformation approach. A mixed effect model (ANOVA) will be fitted by visit (as a categorical covariate) as a fixed effect term and subject as a random effect term. The comparison will begin with Week 17 vs. the average of Weeks 25 through Week 41. If the p-value for Week 17 vs. the average of Week 25 through Week 41 comparison is ≤ 0.05 (i.e. steady state not achieved at Week 17), then the comparison will continue with Week 25 vs. Week 33 through Week 41.
Model Checking & Diagnostics

 Refer to Appendix 12: Model Checking and Diagnostics for Statistical Analyses.
Model Results Presentation

 Statistical analysis of accumulation of plasma CAB following treatment with CAB LA will be presented in tabular format with geometric mean ratios between Week 34 and Week 6, and 90% CIs for the ratios of C_{τ} for CAB. In steady-state analysis, the ratio of Geometric LS means and its 95% CI will be presented for the comparison(s).

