10. STATISTICAL CONSIDERATIONS

10.1. Sample Size Determination

10.1.1. Hypotheses

No formal statistical hypotheses will be evaluated. The study is designed to evaluate the PK, safety, tolerability, and acceptability of the injectable agent, CAB LA (600 mg dose administered at 8-week intervals after 2 initial doses 4 weeks apart) in HIV-uninfected men in China where at least 60% of the men are of a population who have sex with men. Where appropriate, an estimation approach will be taken, and point estimates and confidence intervals will be constructed.

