10.3.1.2. Pharmacokinetic Analysis

Plasma PK parameters will be generated in accordance to Section 9.5.

Concentration-time data summaries should include number (n), mean, standard deviation (SD), coefficient of variation (%CV), geometric mean, geometric mean coefficient of variation (% CV_b), 95% CI, median, minimum, and maximum. Concentration-time data will be summarized using all data for each planned visit regardless of timing as well as for evaluable data that falls within allowable windows for each visit (to be defined in the RAP). Unless stated otherwise, descriptive summaries will include number (n), mean, standard deviation (SD), coefficient of variation (%CV), median, minimum, and maximum for continuous variables, n and percent (%) for categorical variables, and geometric mean, 95% confidence interval (CI), and the between-participant CV (% CV_b) for the log_e-transformed PK parameters.

Accumulation of plasma CAB following CAB LA will be determined by using point estimates and confidence intervals for difference in least squares means for the following comparison:

Comparison	Test	Reference
Accumulation	1 week post injection concentrations Week 34	1 week post injection concentrations Week 6

Time to steady state will be assessed by comparing plasma concentration of CAB at Week 41 (C_{τ} following 5th injection) to previous C_{τ} concentrations at Weeks 17, 25, and 33. This may be accomplished by visual inspection of graphical data or by calculating the point estimate and confidence interval for the slope for $\log(C_{\tau})$ by week for Weeks 25 through 41.

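### SAP 7.3.3.2 reads a non-significant Helmert contrast as steady state, with no margin or precision, and makes the next contrast depend on that p-value

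*SAP*

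**What the plan says.** SAP 7.3.3.2 plans, if data permit, an analysis of log-transformed troughs at Weeks 17, 25, 33 and 41 to "evaluate whether steady state was achieved using the Helmert transformation approach". The model has visit "as a categorical covariate) as a fixed effect term and subject as a random effect term".

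The sequence is as follows:

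- "The comparison will begin with Week 17 vs. the average of Weeks 25 through Week 41".
- A p-value of 0.05 or less is taken to mean that troughs had not reached steady state by Week 17. Only in that event does the SAP go on: "then the comparison will continue with Week 25 vs. Week 33 through Week 41".
- The ratio of geometric least-squares means and its 95% CI are presented for the comparison or comparisons made.

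The section gives no equivalence margin and no precision target. It does not say what is concluded if the second contrast is also significant. It lists no Week 33 versus Week 41 contrast.

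Protocol 10.3.1.2 approaches the question differently. It compares the Week 41 trough with those at Weeks 17, 25 and 33, and allows this either by inspecting graphs or by "calculating the point estimate and confidence interval for the slope for" log trough by week over Weeks 25 to 41. Protocol 10.1.1 disclaims formal hypotheses and adds: "Where appropriate, an estimation approach will be taken, and point estimates and confidence intervals will be constructed".

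SAP 2.1 exists in two versions in the document. One lists only changes to the adverse events of special interest; the other states that nothing changed. Neither mentions the steady-state method.

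**The concern.** The rule attaches a conclusion to each side of p = 0.05. A small p-value is reasonable evidence that the Week 17 trough differs from later ones. A large p-value is not evidence that it equals them: it can mean the troughs agree, or that the data are too variable or too few to show a difference. Because no margin is set, the rule cannot tell these apart, and the chance of reporting steady state rises as the data get worse.

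The same p-value also decides whether the Week 25 contrast is estimated. At stake is a conclusion in the primary pharmacokinetic section of a study whose stated purpose is to confirm dose selection for Phase 3 in Chinese men. How quickly troughs level off should be described by how close they are and how precisely that is known.

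**Working it through.** The documents state no power, precision or error rate for this analysis, and Protocol 10.1.2 gives no calculation behind the 40 participants, so there is no planned figure to reproduce. The check works out how often the rule as written would read a real shortfall as steady state.

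**Inputs**

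- n = 40 on injections (Protocol 10.1.2), complete data.
- Contrast 1: Week 17 minus the mean of three later visits, so the variance factor is 1 + 1/3 = 4/3 (SAP 7.3.3.2).
- Visit fixed and subject random, so the contrast uses the within-subject residual SD, s, with df = 3 × (40 − 1) = 117.
- Two-sided 5% test. Sidedness is not stated; two-sided matches the 95% CI.
- s is **not in the documents**. Protocol Table 3 gives only between-subject variability (CV 54% and 42% for troughs on 600 mg every 8 weeks). Assumed range for s: 0.2, 0.3, 0.4 on the log scale.

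**Formulas**

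SE = s × √(4/3) / √40. The non-centrality is ln(true ratio) / SE. The miss rate is the probability that a non-central t with 117 df falls within ±1.98. With a true ratio of 1, the rule flags 5% of trials, as it should.

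For reference, ln 0.90 = −0.105, ln 0.85 = −0.163 and ln 0.80 = −0.223.

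| | s = 0.2 | s = 0.3 | s = 0.4 |
|---|---|---|---|
| SE | 0.0365 | 0.0548 | 0.0730 |
| Non-centrality, 10% shortfall | −2.89 | −1.92 | −1.44 |
| Read as steady state, 10% shortfall | 18% | 52% | 70% |
| Non-centrality, 15% shortfall | −4.45 | −2.97 | −2.23 |
| Read as steady state, 15% shortfall | 1% | 16% | 40% |
| Non-centrality, 20% shortfall | −6.11 | −4.07 | −3.06 |
| Read as steady state, 20% shortfall | 0% | 2% | 14% |
| Lowest observed ratio still non-significant, exp(−1.98 × SE) | 0.93 | 0.90 | 0.87 |

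Participants lost from the injection phase are not replaced (Protocol 5.2). With an assumed 32 completers, the SE grows by √(40/32) = 1.12 and df = 93. The 10% row becomes 28%, 60% and 75%.

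**How much is due to the stop itself?**

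Contrast 2 (Week 25 versus the mean of Weeks 33 and 41) has variance factor 1 + 1/2 = 1.5. Two profiles were tried with n = 40 and an assumed within-subject CV of 40%, that is s = √ln(1.16) = 0.385.

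- *Troughs rising evenly by 20% from Week 17 to Week 41.* Contrast 1 has true ratio 0.886 and is significant in 40.3% of trials. Contrast 2 has true ratio 0.913 and would be significant in 22.8%. Simulating the sequence, 59.9% of trials are read as steady state at Week 17, 30.9% at Week 25 and 9.2% at neither. The first contrast is the more sensitive, so running the second would seldom rescue the conclusion.
- *True troughs of 1.00, 0.85, 1.00 and 1/0.85 (about 1.18).* Contrast 1 is null and passes 95% of the time. Contrast 2 has ratio 0.784 and would be significant in 90% of trials, but is not run. The stop loses a detectable signal here, though only because the profile is not monotone.

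**The case against.** The strongest reply is that the results are not as bare as the rule suggests. The SAP presents the ratio and 95% CI for each comparison it makes, so a non-significant Week 17 result appears with its size and uncertainty. Whatever the p-value, Table 3.4 summarises concentrations by visit, Table 3.6 summarises log-transformed parameters, and Figures 3.5 and 3.6 show individual and median troughs by week. A reader might infer that a shortfall would be concealed; the documents do not support that. What the gate withholds is one model-based contrast, Week 25 versus Weeks 33 and 41. Week 33 versus Week 41 is missing under any p-value, so the gate is not the cause.

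A reader might also infer that the SAP breaks a protocol commitment to estimation. It does not. The protocol's wording is permissive: it offers graphs as an alternative to the slope, qualifies estimation with a where-appropriate clause, and leaves full details to the analysis plan. Figures 3.5 and 3.6 meet the graphical option. What remains is that a change of method is not recorded in SAP 2.1.

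Third, the miss rates depend on an assumed SD, and nothing in the documents says that 10% or 15% matters. Protocol 5.5 reports that a one-week delay lowers the median simulated trough from 1.35 to 1.08 µg/mL, a 20% drop, and treats that as supporting a maximum one-week delay. At 20% the rule misses at most 14% over the assumed range. This is fair, and it limits the practical weight of the point. It also shows the gap: the SAP names no difference that matters, so its p-value cannot be read against one.

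Finally, no dosing decision within the trial turns on this result. That limits the consequence but does not make the inference sound.

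**Conclusion.** The concern holds, with limits. SAP 7.3.3.2 infers steady state from p above 0.05 with no margin or stated precision, and estimates the Week 25 contrast only when the first is significant. With 40 participants, a true 10% shortfall at Week 17 would be read as steady state about 18%, 52% or 70% of the time, and a 15% shortfall about 1%, 16% or 40%. These figures rest on an assumed within-subject log SD of 0.2, 0.3 or 0.4, a two-sided test and complete data. At the low end a 15% shortfall is almost always detected, so the size of the problem depends on a quantity the documents do not give.

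It would be tempting to blame the stopping step. For steadily rising troughs that is not supported: the first contrast is then the more powerful, and the main fault is what is read into p above 0.05. The stop matters for non-monotone profiles. The defect lies in the stated conclusion and in one conditional estimate; the underlying trough data are reported in any case.

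**What to change.** In SAP 7.3.3.2:

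- Remove the p-value gate.
- From the same mixed model, always report the geometric mean ratios of Weeks 17, 25 and 33 to Week 41, each with its CI.
- Add the slope of log trough over Weeks 25 to 41 with its CI, which is one of the protocol's two options.
- Base the steady-state statement on those estimates and intervals, and say that p above 0.05 is not taken as evidence of steady state.
- Record the departure from the protocol's method in SAP 2.1.

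The cost is a few contrast lines in Table 3.8 and revised wording; no participants, visits or samples are added. The downside is a less clear-cut yes-or-no statement about when steady state was reached.

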Secondary Endpoint	
 Plasma CAB AUC(0-τ), C_{max}, C_{τ}, t_{max}, λ_z, t_{1/2}, CL/F, and Vz/F through Weeks 5-89. Safety and tolerability parameters, including adverse events, study withdrawals due to AEs, vital signs assessments, and clinical laboratory assessments, for oral lead-in phase (Day 1 to Week 4). Injection discontinuation rate, the number and severity of ISRs and additional acceptability measures. Evaluation of relationships between significant safety and tolerability

Overview	Key Elements of the RAP
	parameters and CAB PK may be explored.
Study Design	
 • This will be an open label, non-randomized, single arm study. Participants will receive daily oral CAB (30mg tablets) for 4 weeks during the Oral Phase of the study and intramuscular (IM) injections of 600 mg of CAB LA at Week 5, Week 9, Week 17, Week 25 and Week 33. • Starting at 8 weeks post last injection, participants will be seen once every 12 weeks for 48 weeks during the follow-up phase. • Subjects who volunteer to participate in the intensive PK assessment will have serial blood sampling for measurement of plasma CAB concentrations following oral administration over a 24 h window starting on Day 27 and ending on Day 28 • PK samples at trough for Oral Phase will be collected for all subjects prior to dose within 20 to 28 hours following oral administration the day prior; Intensive oral PK samples will be collected from approximately 16 participants. • PK Samples for Injection Phase will be collected prior to CAB LA injections at Week 5, 9, 17, 25, and 33 with the exception of 1-week post injection samples at Weeks 6, 10, 18, 26, 34, 37 (4-week post injection sample) and Week 41 • Long-term follow up PK samples will be collected at Week 53, 65, 77, and 89.
Planned Analyses	
 • The primary safety analysis and PK analyses including both oral phase and injection phase through Weeks 5 to 41 will be performed after all ongoing participants complete the Week 41 visit or withdraw from the study treatment, whichever comes first. • The end of study analysis will be performed after all ongoing participants complete the Week 89 visit or withdraw from the study treatment, whichever comes first.

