10.11. Appendix 11: Multiple Comparisons & Multiplicity

10.11.1. Handling of Multiple Comparisons & Multiplicity

Not applicable.

10.12. Appendix 12: Model Checking and Diagnostics for Statistical Analyses**10.12.1. Statistical Analysis Assumptions**

Endpoint(s)	
• PK endpoint C_{τ}
Analysis	
• ANOVA (primary)
	
• Model assumptions will be applied, but appropriate adjustments maybe made based on the data.• The Kenward and Roger method for approximating the denominator degrees of freedom and correcting for bias in the estimated variance-covariance of the fixed effects will be used.

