10.14.8. Pharmacokinetic Tables

Pharmacokinetic : Tables					
No.	Population	IDSL / TST ID / Example Shell	Title	Programming Notes	Deliverable [Priority]
Oral Phase					
3.1	Oral PK	PKCT1	Summary of CAB Plasma Pharmacokinetic Concentration-Time Data – Oral Phase		SAC [1]
3.2	Oral PK	PKPT4	Summary of Derived CAB Plasma Pharmacokinetic Parameters (Non-Transformed) – Oral Phase	Parameters with units	SAC [1]
3.3	Oral PK	PKPT4	Summary of Derived CAB Plasma Pharmacokinetic Parameters (Log-Transformed) – Oral Phase	Parameters with units	SAC [1]
Injection Phase (up to Week 41)					
3.4	Injection (Week 41) PK	PKCT1	Summary of CAB Plasma Pharmacokinetic Concentration-Time Data – Injection Phase (up to Week 41)		W41 SAC [1], SAC [1]
3.5	Injection (Week 41) PK	PKPT4	Summary of Derived CAB Plasma Pharmacokinetic Parameters (Non-Transformed) – Injection Phase (up to Week 41)	Parameters with units	W41 SAC [1], SAC [1]
3.6	Injection (Week 41) PK	PKPT4	Summary of Derived CAB Plasma Pharmacokinetic Parameters (Log-Transformed) – Injection Phase (up to Week 41)	Parameters with units	W41 SAC [1] SAC [1]
3.7	Injection (Week 41) PK	PKPT3	Statistical Analysis of CAB Plasma Accumulation – Injection Phase (up to Week 41)	$C\tau$ only for Injection Phase at Week 41.	W41 SAC [1], SAC [1]
3.8	Injection (Week 41) PK	PKPT3	Statistical Analysis of CAB Plasma Steady-state Pre-dose Concentrations – Injection Phase (up to Week 41)	$C\tau$ only for Injection Phase at Week 41.	W41 SAC [1], SAC [1]

Pharmacokinetic : Tables					
No.	Population	IDSL / TST ID / Example Shell	Title	Programming Notes	Deliverable [Priority]
Injection Phase (up to Week 89)					
3.9	Injection (Week 89) PK	PKCT1	Summary of CAB Plasma Pharmacokinetic Concentration-Time Data – Injection Phase (up to Week 89)		SAC [1]
3.10	Injection (Week 89) PK	PKPT4	Summary of Derived CAB Plasma Pharmacokinetic Parameters (Non-Transformed) – Injection Phase (up to Week 89)	Parameters with units	SAC [1]
3.11	Injection (Week 89) PK	PKPT4	Summary of Derived CAB Plasma Pharmacokinetic Parameters (Log-Transformed) – Injection Phase (up to Week 89)	Parameters with units	SAC [1]

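### The accumulation analysis in SAP 7.3.3.2 names Cτ and AUC(0-τ) at Weeks 6 and 34, where neither is measured; the protocol metric is the 1-week post-injection concentration

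*SAP*

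**What the plan says.** **Protocol 10.3.1.2** estimates accumulation from a difference in least squares means. The test condition is "1 week post injection concentrations Week 34" and the reference is the same quantity at Week 6.

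**SAP 7.3.3.2** gives three descriptions of one analysis:

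- Response: "To determine accumulation of plasma CAB following treatment with CAB LA, the log-transformed" Cτ values are the outcome of a mixed model with visit as a fixed effect and subject as a random effect.
- Contrast: "accumulation of CAB based on" AUC(0-τ), written as Week 34 / Week 6.
- Output: results are tabulated "with geometric mean ratios between Week 34 and Week 6, and 90% CIs for the ratios of" Cτ.

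**SAP 7.3.3.1, Table 10**, defines Cτ as "Observed concentration at the end of the dosing interval, determined directly from the concentration-time data". The synopsis of the same SAP says that injection-phase samples are pre-injection "with the exception of 1-week post injection samples at Weeks 6, 10, 18, 26, 34", and it then adds Weeks 37 and 41.

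**SAP 10.14.8** lists Table 3.7, "Statistical Analysis of CAB Plasma Accumulation", with a programming note restricting it to Cτ at Week 41. The note for Table 3.8 (steady state) is identical. Appendix 12 names Cτ as the only PK endpoint for the ANOVA.

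**SAP 2.1** declares only changes to the adverse events of special interest. The earlier SAP version in the same file has the same accumulation text and states that nothing departs from the protocol.

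**The concern.** Accumulation is one of two statistical models in the primary PK analysis; the other is attainment of steady state. Its response variable is named inconsistently, and neither named metric belongs to the stated visits. A Week 6 or Week 34 concentration is taken one week after dosing, near the peak, while Cτ is by definition the trough. AUC(0-τ) describes a whole interval, not a visit.

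A programmer working from the SAP alone cannot compute the stated ratio. The plausible substitutes answer different questions: some would compare an 8-week interval with a 4-week one, so that interval length is mixed with accumulation. The published ratio could then differ from the protocol's quantity in size and even in direction, without any declared change.

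**Working it through.** **1. Which visits yield Cτ.** Injections are at Weeks 5, 9, 17, 25 and 33. PK samples up to Week 41 are at Weeks 5, 6, 9, 10, 17, 18, 25, 26, 33, 34, 37 and 41.

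| Interval | Length | Samples (weeks after dose) | Cτ visit |
|---|---|---|---|
| Weeks 5–9 | 4 weeks | 0, 1, 4 | Week 9 |
| Weeks 9–17 | 8 weeks | 0, 1, 8 | Week 17 |
| Weeks 17–25 | 8 weeks | 0, 1, 8 | Week 25 |
| Weeks 25–33 | 8 weeks | 0, 1, 8 | Week 33 |
| Weeks 33–41 | 8 weeks | 0, 1, 4, 8 | Week 41 |

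Neither Week 6 nor Week 34 is a Cτ visit. Week 6 is 1/4 = 25% of the way through its interval, and Week 34 is 1/8 = 12.5%. Protocol 10.3.1.2 itself names Week 41 as the Cτ visit after the fifth injection.

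**2. How far apart the metrics are.** Protocol 5.5 predicts steady-state medians for the 1-week concentration and for Cτ. The ratio is 4 / 1.35 = 2.96 with normal UGT function and 5.5 / 1.8 = 3.06 with reduced function. A 1-week concentration is therefore about three times Cτ.

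**3. What a remapping would do (illustration only).** The SAP does not state this reading. Suppose the analyst takes Week 6 to mean the interval Weeks 5–9 and Week 34 to mean Weeks 33–41.

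Each dose is assumed to contribute ka/(ka − ke) × [exp(−ke·t) − exp(−ka·t)], and the five doses are added. Residual oral CAB is ignored.

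Absorption half-life is days × ln 2 / ln(Cmax/Cτ), using the decline from about one week after dosing to the end of the interval:

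- ECLAIR, W24–W36: 77 × ln 2 / ln(4.91/0.387) = 21.0 days
- Protocol simulation: 49 × ln 2 / ln(4/1.35) = 31.3 days
- LATTE-2, W40–W48: 49 × ln 2 / ln(3.33/1.49) = 42.2 days

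Elimination half-life is an assumption with a range of 26 to 41 h. The lower value follows from the oral figures if Cmax and Cτ are taken as 22 h apart: 22 × ln 2 / ln(7.5/4.2) ≈ 26 h. The upper value is assumed.

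| Absorption half-life | Protocol metric, C(W34)/C(W6) | Cτ, W41/W9 | AUC(0-τ), W33–41 / W5–9 |
|---|---|---|---|
| 21.0 d | 1.19–1.20 | 0.47 | 1.72–1.76 |
| 31.3 d | 1.42–1.44 | 0.76 | 2.26–2.32 |
| 42.2 d | 1.67–1.71 | 1.05 | 2.84–2.92 |

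Where a cell shows a range, it runs from the 26 h to the 41 h elimination half-life. Dividing the AUC ratio by 8/4 = 2 gives 0.86 to 1.46 per unit time. In every row the mapped Cτ ratio lies below the protocol metric and the mapped AUC ratio lies above it. In two of three rows the mapped Cτ ratio is below 1 although the 1-week concentrations accumulate.

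**The case against.** The strongest reply is that only the label is wrong. Concentrations are collected at both visits. The SAP keeps the protocol's visits, their order, the log-ratio form and visit as a fixed effect. An analyst who fits the model to whatever was measured at Weeks 6 and 34 obtains the protocol's ratio, and one who consults the protocol can see what was meant. This stands, and it argues for a drafting error rather than a chosen new metric. On that reading, the missing declaration in SAP 2.1 is secondary to the contradiction inside 7.3.3.2.

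It is also fair that the numerical ranges apply only to a mapping the SAP never states, and that they rest on two-point half-lives from different studies and regimens. They illustrate direction and do not measure a committed error. No hypothesis, sample size or decision rule depends on the ratio.

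The SAP's proviso that the analysis runs only if sufficient data are available does not help, because the gap comes from the sampling schedule, not from lost samples. The 90% confidence level is not a contradiction either, since the protocol gives no level for this comparison.

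None of this makes the SAP text executable: the response, the contrast and the Table 3.7 note all point away from the protocol metric.

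**Conclusion.** The concern holds. SAP 7.3.3.2 specifies a Week 34/Week 6 ratio of Cτ, partly described as AUC(0-τ), at two visits where by the SAP's own definition and schedule there is no Cτ and where a single sample is not an AUC. The protocol's metric is not named anywhere in the SAP's accumulation text, and SAP 2.1 does not declare a change. This conclusion needs only the documents.

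The possible numerical effect depends on the assumed half-lives and on an unstated mapping. With those, the substitutes fall on either side of the protocol ratio and one can reverse its direction. Because the ratio is descriptive and remains estimable from scheduled samples, the point is one to fix before analysis, not a threat to the trial. The steady-state analysis, which uses Cτ at Weeks 17, 25, 33 and 41, is unaffected.

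**What to change.** - **SAP 7.3.3.2:** state the accumulation response as the log-transformed 1-week post-injection concentration, with contrast Week 34 versus Week 6. Remove Cτ and AUC(0-τ) from the accumulation model and its results text.
- **Table 3.7 programming note:** replace the Cτ/Week 41 wording with the 1-week post-injection concentration at Weeks 6 and 34.
- **Appendix 12:** add this endpoint and keep Cτ for the steady-state model.
- **If another metric is really intended:** declare it in SAP 2.1 and compare intervals of equal length. Only Weeks 5–9 lasts 4 weeks, so such a comparison could start no earlier than Weeks 9–17, after two doses, and would not measure accumulation from the first dose.

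The cost is a few lines of SAP text and one programming note. No new data or visits are needed.
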